### First two weeks – daily phone calls

#### **Baseline**

Good morning/afternoon I am \_\_\_\_\_ from the University of Michigan Mott Children's hospital. The purpose of this call is to follow up with you regarding you or your child's experience with the ssNPA last night.

Did you fill out the daily survey from last night?

*\*If yes\* [skip to the bottom to the adverse events evaluation]*

*\*If no\* Alright, well then I have a few questions to ask you.*

Did you have any difficulty with using the ssNPA last night? *\*If answers yes\* Could you describe those difficulties to me?*

How long did your child use the ssNPA last night?

How did your child tolerate the device?

Did you have to re-insert or re-adjust the device during the night? If so, how many times did you have to get up to do this?

What was the level of perceived comfort of your child as they wore the device during the night or, if applicable, during the day.

Did the frequency and/or amplitude of your child's snores change last night?

Did you notice any apneas during the night?

How did your child sleep overall?

Does your child seem more rested today?

Did you have any difficulties or adverse events with the device? Did you notice any nosebleeds, irritation, or any of the adverse events listed on your instruction form during your child's use of the device?

Tonight, you will insert the ssNPA device again for overnight use. Remember that if your child feels comfortable with the device in place in the morning, you can leave it in place during the daytime as well. Please fill out the daily survey and we will call you tomorrow to follow-up with you as well.

Do you have any other comments/concerns/questions?

Thank you for your time.

---

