Families will return to the clinic at weeks 2 and 4 to ensure optimal care and evaluate the device safety, tolerability, and acceptability. In between the clinic visits, regular contact will be made with families by the team, daily during the first week and weekly by the 2nd week (see Appendices H-K). During these calls, caregivers will report night to night witnessed apneas, improvement in daytime awareness, improvement in sleeping patterns of the patient, and any adverse events. Beside the two clinical visits at 2nd and 4th week, the number and frequency of extra visits will depend on: (1) the child's current threshold; and (2) how the child and family advance through each step of the desensitization protocol. The decision to hold on a particular step of the desensitization program will be based on whether the child's current level of anxiety or opposition is elevated. A recommendation to discontinue ssNPA treatment may be made if the child or family do not make progress with wearing the device in 2-4 weeks (depending on the number of visits during that time). Discontinuation of ssNPA therapy may occur after case consultation with other members of the study team to ensure that all strategies have been considered.

Evaluation of the device safety, tolerability, and acceptability will be assessed by a survey of patients and caregivers using a validated questionnaire with 10-point response scale (Appendix K). Mean and standard deviation scores as well as the percentage of those reporting satisfactory or better will be assessed. Device safety will be determined by adverse events

Table 3. Milestones for successful completion of the R61 phase

R61 Milestones	Goal (out of 5 subjects)
1. Device optimization and manufacturing in clean/sterile manner	100%
2. Parent report of ease of insertion; $\geq 5$ on Likert scale of 1-10	60% (3 of 5)
3. Child able to tolerate device in place	60% (3 of 5)
4. Child able to maintain device in place during sleep	60% (3 of 5)
5. Parent report of adherence based on diary	60% (3 of 5)
6. Comfort rating $\geq 6$ on Likert scale of 1-10	60% (3 of 5)

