#### *9.4.1 Active group (ssNPA):*

Children randomized to the ssNPA device will have a device length sized and fitted by an otolaryngologist as described in the R61 phase. Families will be instructed on use of the ssNPA and an experienced nurse will assist each family with our desensitization protocol. Briefly, this will include an overview of the ssNPA and have the child and parent handle the device. If no child anxiety the parent will be requested to insert the ssNPA. A timetable will be agreed upon with dates when to move to the next step. Parents will be taught how to clean the device and will be educated and provided with handouts regarding safety and hygiene concerns. Children will be encouraged to use the ssNPA for 8 weeks, at which time a PSG will occur for primary outcome assessment. During these 8 weeks, regular contact will be made with families by the team to make sure they are comfortable with using the device. We will make daily contact during the first week of using the device and will continue during following weeks if needed. We will also ask parents/caregivers to send us a photo of the child wearing the ssNPA before parents go to bed and also in the morning. A sleep diary will also need to be filled out every day during these 8 weeks to report the child sleep and wake up time. After the 8-week PSG, the active group will continue wearing the ssNPA for another 8 weeks and have the final PSG at Week 16. The families will complete several validated assessment tools same as the baseline visit for comparison of subjective endpoints at the end of each 8-week period. Subjects and families will be notified that consent to participate is voluntary and can be withdrawn at any time.

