Another important parameter is adherence, which will be reported as percentage of participants using the device at two months after initiation in both the active group (ssNPA) and in the wait list group (SoC) participants who received the device at Month 2. In the active group, we will compare adherence rates between treatment responders (those with >50% reduction in AHI and AHI<15 at Week 8) and non-responders to assess the relationship between adherence and treatment response. However, since clinically meaningful improvement can be accomplished by using ssNPA without the need for continued use of the device for two months, we will carefully analyze the daily

adherence data obtained using diaries to have a better understanding of the relationship between adherence during the first 8 weeks and treatment response.

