### Weeks 3-8 – weekly phone calls

Good morning/afternoon I am \_\_\_\_\_ from the University of Michigan Mott Children's hospital. The purpose of this call is to follow up with you regarding you or your child's experience with the ssNPA over the past week.

Did you fill out the weekly survey for this week?

*\*If yes\* [skip to the bottom to the adverse events evaluation]*

*\*If no\** Alright, well then I have a few questions to ask you.

Did you have any difficulty with using the ssNPA over this past week? *\*If answers yes\** Could you describe those difficulties to me?

On average, how long did your child use the ssNPA each night/day?

How has your child been tolerating the device?

Did you have to re-insert or re-adjust the device during the night? If so, on average how many times did you have to get up to do this?

What was the level of perceived comfort of your child as they wore the device during the night or, if applicable, during the day.

Did the frequency and/or amplitude of your child's snores change over the week?

Did you notice any apneas during the night?

How has your child been sleeping overall?

Does your child seem more rested during the day?

Did you have any difficulties or adverse events with the device? Did you notice any nosebleeds, irritation, or any of the adverse events listed on your instruction form during your child's use of the device?

Any other comments or concerns about usage that you would like to bring up?

Thank you very much for your time. I will follow up with you again next week.

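### Completing the survey skips the only visible call questions on duration of device use and witnessed apneas, and the surveys contain neither item

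*Combined protocol and SAP*

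**What the plan says.** Appendix H has one call script for the first two weeks (daily) and one for weeks 3 to 8 (weekly). Each opens by asking whether the survey was done; the weekly version is "Did you fill out the weekly survey for this week". If it was, the caller must "skip to the bottom to the adverse events evaluation". If not, the caller works through a block of questions. In the daily script that block includes "How long did your child use the ssNPA last night" and "Did you notice any apneas during the night". The weekly script has the same apnea question and, for wear time, "On average, how long did your child use the ssNPA each night/day".

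Other sections rely on this information:

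- Section 4.4 makes caregiver-noted, night-to-night witnessed apnea (together with sleep disturbance) the first R33 secondary objective, and adherence the second.
- Section 9.2, Stage 2, states without condition: "During these calls, caregivers will report night to night witnessed apneas".
- Section 10.2.2 reports adherence as the share of participants using the device two months after starting. It also plans to examine daily "adherence data obtained using diaries to have a better understanding of the relationship between adherence during the first 8 weeks and treatment response".
- Table 3 and Section 10.3.1 set a diary-based adherence milestone for R61 (60%, 3 of 5).
- Section 9.4.1 describes the diary as follows: "A sleep diary will also need to be filled out every day during these 8 weeks to report the child sleep and wake up time". It also asks R33 active-arm families for bedtime and morning photos of the child wearing the device.

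**The concern.** A skip of this kind is harmless if the survey has already asked the skipped questions. Here it has not. Duration of use and witnessed apneas would be recorded only for nights or weeks when the survey was not completed, so the families who cooperate best supply the least information. Whether these data are missing then depends on survey compliance and not on chance.

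At stake are the witnessed-apnea part of a stated secondary objective and the record of how long the device was worn. Nights that are not recorded cannot be recovered later.

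**Working it through.** The plan states no figure that depends on this point, so there is none to reproduce. The check is an item-by-item comparison, followed by a simple illustration of coverage.

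**1. Where each item is asked**

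| Instrument | Duration of use | Witnessed apneas |
|---|---|---|
| Daily call script (App. H) | Only if survey not done | Only if survey not done |
| Weekly call script (App. H) | Only if survey not done; weekly average | Only if survey not done |
| Day-one survey (App. I, 12 items) | No | No |
| Daily survey (App. J, 11 items) | No | No |
| Weekly survey (App. K, 11 items) | No | No |
| Final questionnaire (App. M) | No; asks only likelihood of use | No |
| Diary, as described in 9.4.1 | Not described | Not described |
| Photos (9.4.1, R33 active arm) | Device in place at two moments | No |

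The surveys cover insertion, tolerance, complete and partial dislodgement, times the caregiver got up, comfort, restfulness, snoring and tiredness.

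**2. Share of calls that yield the data**

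Under Appendix H, calls per child = 14 daily (two weeks) + 6 weekly (weeks 3 to 8) = 20. Let c be the proportion of calls for which the survey was completed. The documents give no value, so c is an assumption and is shown over a range. Calls with duration and apnea data = 20 × (1 - c).

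| c | Calculation | Calls with data |
|---|---|---|
| 50% | 20 × 0.5 | 10 |
| 70% | 20 × 0.3 | 6 |
| 80% | 20 × 0.2 | 4 |
| 90% | 20 × 0.1 | 2 |
| 100% | 20 × 0 | 0 |

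Section 9.2 gives a different contact schedule (daily in week 1, weekly from week 2). The number of calls would change under it, but the share 1 - c would not. If both questions lay outside the skip, every answered call would yield them, whatever c is.

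**3. Comparator for improvement**

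No baseline apnea item is visible. Section 9.4.2 describes the calls to standard-of-care families only as a means of retention. Section 10.2.2 does not name witnessed apnea among the outcomes it compares.

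**The case against.** The strongest reply is that adherence does not rest on these calls. The reported measure needs use or non-use at two months, not hours, and in the R33 active arm the bedtime and morning photos can show it. Read with diary sleep and wake times and the dislodgement items, the photos even allow a rough estimate of nightly wear. This stands. A reader might infer from the skip that adherence cannot be measured at all; the documents do not support that. The photos are, however, described only for the R33 active arm. None are described for R61, and for wait-list children who start at Week 8 the text says only that contact will be as already detailed.

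A reader might also infer that the diary holds nothing but sleep and wake times. That goes too far. No diary form is shown, and Table 3 and Sections 10.2.2 and 10.3.1 treat the diary as an adherence source. What can be said is that its one description does not match that use. Appendices F and G and the standard sleep questionnaires are not in the text reviewed, so a wear log or an apnea item there cannot be excluded. A questionnaire given at baseline and at the end of each 8-week period would still not give night-to-night data.

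Third, Section 9.2 cites these appendices but the R33 active-arm text does not, and refining the surveys for the larger study is itself an R61 objective. The R33 instruments may therefore differ. That is fair, but no other call script is shown, and the conflict with Section 9.2 exists in R61 regardless.

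Finally, it is tempting to say that missed-survey nights are the less adherent ones and to give the bias a direction. Nothing in the documents establishes this.

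**Conclusion.** The skip, followed as written, contradicts Section 9.2. Families who complete every survey give no witnessed-apnea or wear-duration data through the calls or surveys. For them, the night-to-night witnessed-apnea part of the first R33 secondary objective has no visible source; the sleep-disturbance part is covered by other items. Coverage through the calls is 1 - c, from half of calls at c = 50% to none at c = 100%, and missingness is tied to survey compliance.

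The two-month adherence percentage remains supportable in the R33 active arm. The diary's description and its use as an adherence source must be reconciled. The primary AHI endpoint, measured by polysomnography, is unaffected. The conclusion assumes that the scripts are followed as printed, that the R33 calls use them, and that no unseen form collects these items.

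**What to change.** - Move the duration-of-use and witnessed-apnea questions outside the skip in both scripts so that every caregiver is asked, or add both items to Appendices I, J and K.
- Include a device-use field in the diary, so that it can supply the daily adherence data used in Section 10.2.2 and the R61 milestone, and align the description in Section 9.4.1 with it.
- Ask the same short witnessed-apnea item at baseline and in the existing standard-of-care calls, so that improvement has a comparator.

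Even when every caregiver is asked, the weekly calls in weeks 3 to 8 give weekly rather than nightly reports. The wording of the objective should match the frequency of collection finally chosen.

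The cost is a revision of forms and scripts with IRB notification, and slightly longer caregiver contacts. No extra visits or participants are needed. The frequency of the standard-of-care calls is not stated, and it will limit how fine the comparison can be.

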### 9.3 Schedule of Events Table

	Screen	Day 0	Week 1-2	End of Week 2	Week 3-4	End of week 4	Weeks 5-8	At 8 th week (approx)
Informed Consent		X						
Medical Hx/Medication Hx	X							X
Vital Signs/Physical Assessment	X							X
Clinical Laboratory Tests (eg polysomnography)	X							X
Baseline questionnaires		X						
Device placement		X						
Parent training		X						
At home device use			X		X		X	
Device tolerability surveys			X		X		X	X
Clinic visit				X		X		X
Adverse events evaluation (through daily/weekly phone calls)			X		X		X	X
Sleep and QoL surveys		X						X
Overnight sleep study								X

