## **9.5 TREATMENT INTERRUPTIONS-DISCONTINUATION CRITERIA**

### ***9.5.1 Treatment Interruption Criteria***

In the event of patient illness, the patient will temporarily stop study treatment. Because nasal secretions and other upper respiratory symptoms can interfere with accurate data measurement and observation of treatment, the patient will have the option of pausing using the device until symptoms subside. Alternatively, if caregivers feel the device is providing symptomatic relief during the concurrent illness, they may continue use – however assessments, such as PSG will be postponed until resolution of acute illness to minimize artifact. Additionally, in the event of any temporary family emergency or necessary situation, the patient may also temporarily stop using the device. If for some reason there is a need for a different sized device, the treatment maybe paused while the new device is manufactured and delivered to the family. Observation will resume once the patient is treated with the new device.

The decision to hold on a particular step of the desensitization program will be based on whether the child's current level of anxiety or opposition is elevated. A recommendation to discontinue ssNPA treatment may be made if the child or family do not make progress with wearing the device in 2-4 weeks (depending on the number of visits during that time). Discontinuation of ssNPA therapy may occur after case consultation with other members of the study team to ensure that all strategies have been considered.

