#### ***11.4.2 Principal Investigator Responsibilities***

The Principal Investigator (PI) will promptly review documented adverse effects and abnormal test findings to determine 1) if the abnormal test finding should be classified as an adverse effect; 2) if there is a reasonable possibility that the adverse effect was caused by the investigational device or, if applicable, other study treatment or diagnostic product(s); and 3) if the adverse effect meets the criteria for a *serious adverse effect*.

In accordance with 21 CFR Part 812.150(a)(1) and (b)(1), the PI shall promptly report the results of an evaluation of any serious and unanticipated adverse device effect to the University of Michigan IRBMED as soon as possible, but not later than 10 working days after the PI first receives notice of the effect. Thereafter, the PI shall submit such additional reports concerning the effect to the sponsor of the trial and as the FDA requests. Complications and non-serious or anticipated adverse events should be documented and tabulated but need not be submitted by the PI to the sponsor of the trial or the FDA as individual reports.

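### The scripted adverse-event question on the caregiver calls is tied to the device, narrower than the unrestricted collection that section 9.2 describes

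*Combined protocol and SAP*

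**What the plan says.** Section 9.2 (Stage 2) lists what caregivers report on the calls and includes adverse events with no qualifier. The table in section 9.3 has a row headed "Adverse events evaluation (through daily/weekly phone calls").

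Appendix H holds two scripts, one for daily calls in the first two weeks and one for weekly calls in weeks 3 to 8. Both put the same two-sentence prompt to the caregiver. The first sentence is "Did you have any difficulties or adverse events with the device". The second asks whether the caregiver noticed nosebleeds, irritation "or any of the adverse events listed on your instruction form during your child's use of the device". If the family has completed the survey, the caller is told to "skip to the bottom to the adverse events evaluation". The daily script then closes with "Do you have any other comments/concerns/questions"; the weekly script closes with "Any other comments or concerns about usage that you would like to bring up".

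Section 11.4.2 has the PI decide "if there is a reasonable possibility that the adverse effect was caused by the investigational device". The adverse event form (Appendix L) carries a relatedness scale that extends to definitely unrelated, and lists hospitalization among its seriousness categories. Section 9.5.1 provides that during illness "the patient will have the option of pausing using the device until symptoms subside".

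**The concern.** A caregiver who answers the first sentence literally must decide whether an event belongs to the device before mentioning it. The plan reserves that decision for the PI, who can classify only what has been reported. A chest infection or a hospital stay while the device was paused could be left out by a caregiver answering quite truthfully.

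Safety is part of the R61 primary objective (section 4.1), and section 11.4.1 judges the safety of the device from the adverse-event evaluation. The stopping criteria turn on very few patients: more than 2 in section 9.5.2 and more than 1 in section 9.5.3. With thresholds that low, a single relevant event that goes unreported could decide whether one is reached.

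**Working it through.** The point concerns wording, and the plan gives no figure to reproduce. The check sets the texts side by side.

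1. **Intended scope against scripted scope.** Section 9.2: adverse events, unrestricted. Appendix H, both scripts: first, events connected with the device; second, named or listed events during its use. The scripted scope is narrower.

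2. **Who attributes.** Sections 11.4.1 and 11.4.2: the PI. First sentence of the prompt: the caregiver, implicitly. Second sentence: the caregiver only has to recognise an event, so no attribution is needed. The shift of causality judgement is therefore partial.

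3. **What the record is built to hold.** Appendix L has categories for events unlikely to be related and definitely not related. The form expects events that the first sentence of the prompt does not ask for.

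4. **Other scripted prompts.**
   - Surveys (Appendices I, J and K): no adverse-event item; the free text concerns experience with the ssNPA.
   - Final questionnaire (Appendix M): comments are about the device.
   - Skip instruction: for families who completed the survey, the device-tied question is the only adverse-event prompt on the call.
   - Closing question: open in the daily script, limited to usage in the weekly script. Weeks 3 to 8 are six of the eight weeks of home use, and that is where the gap is widest.

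5. **Seriousness.** Hospitalization is a seriousness category in Appendix L. Neither script and none of the surveys asks about a hospital stay or an urgent visit.

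6. **Unscripted routes.**
   - Clinic visits at weeks 2, 4 and 8, with medical and medication history and physical assessment at week 8 (sections 9.2 and 9.3). The adverse-event row in section 9.3 is not marked in the end-of-week-2 or end-of-week-4 columns. Where sections 9.2 and 11.4.1 mention evaluation at visits, they speak of possibly related events.
   - Events observed by the investigator or reported by the subject are recorded on the case report forms (section 11.4.1).
   - Medical record and study team are listed as sources in Appendix L.
   - Families may contact a clinician at any hour (section 11.4.1).

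   None of these is a neutral, structured question put to every family.

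7. **Size.** A calculation would need the true event risk, the share of events missed by the scripted question, and the share of those recovered by the routes in step 6. The documents give none of the three, so no detection percentage is offered.

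**The case against.** The strongest reply is that the plan does not depend on this one question. The daily script ends with an unrestricted question that is reached even after the skip. Clinic visits, investigator observation and medical records can bring in events that nobody attributed to the device. The safety plan in section 11.4 is aimed at related events, and section 11.4.1 does not send non-serious unrelated events onward. Much of this stands, and it rules out several stronger readings that a reader might infer:

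- *Off-device or unrelated events are never elicited.* The open closing question and the routes above contradict this. The gap is in systematic elicitation.
- *Device safety will look better than it is.* Leaving out truly unrelated events does not flatter the device. Bias arises only from related events that caregivers fail to attribute, and their frequency is unknown.
- *Children who paused the device are asked less often.* Nothing in section 9.5.1 suspends the calls, and it postpones the sleep study until acute illness resolves, so the team must learn of illness around that time.
- *All off-device events are excluded by the wording.* Reference to the child's use of the device may mean the whole home-use period. Nosebleeds are prompted by name, so a bleed after removal may well be reported. The instruction form's list is not visible in the reviewed text, so its coverage cannot be checked.
- *The fault applies in both phases.* Appendix H is cited in the R61 procedures. Sections 9.4.1 and 9.4.2 describe contact in R33 without naming these scripts.

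The limits on onward reporting do not remove the mismatch, because the PI has to hear of an event before deciding that it is unrelated.

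**Conclusion.** The concern holds as a mismatch between section 9.2 and Appendix H. The only scripted adverse-event prompt is tied to the device, is narrower than the collection the plan describes, and partly asks caregivers to attribute events before the PI does. Ascertainment through the calls is incomplete for events that caregivers regard as unrelated and, on the narrower reading of use, for events while the device is out. It is weakest in weeks 3 to 8 and for urgent visits and hospital stays.

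The size of the loss is unknown. The conclusion assumes that callers follow the scripts as written and that no other adverse-event script is in use; none appears in the documents. This is a cheap improvement to safety ascertainment, worth making, and the documents do not show that the safety results will be materially biased.

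**What to change.** In both Appendix H scripts, ask first: *Since our last call, has your child had any new or worse health problem, injury, urgent or emergency visit, hospital stay or new medicine, whether or not the device was in place and whether or not you think it is related?* Keep the device-specific and listed-event prompts as the second step, and make sure the skip instruction leads to the neutral question. Relatedness stays with the PI, as already planned. If these scripts are also used in R33, use the same wording there.

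The cost is one added question in two scripts and some extra logging of minor unrelated events. No visit, endpoint or clinical rule changes.
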